2.5 Standardization of co-interventions

To minimize the potential for co-interventions and detection bias, we will promote adherence to evidence-based perioperative management in accordance with national and international guidelines, as summarized below. Data on co-interventions will be collected, but non-adherence to these measures will not be considered a protocol violation. Where available, the perioperative and thrombosis services will continue to follow patients as per routine clinical practice. This includes assessment of signs and symptoms of VTE, arterial cardiovascular events, and bleeding. For the duration of the study period, the study team will follow patients. The study team will assume the responsibility for initiating and managing the assigned thromboprophylaxis in the interventional arm. The study team will remain in communication with the treating team.

2.5.1 Preoperative VTE prophylaxis

The American Society of Hematology (ASH) 2019 guidelines and American College of Chest Physicians recommend - Prophylactic UFH or LMWH before surgery. The last dose should be administered at least four hours before the procedure.^{7,19}

2.5.2 Intra-operative bleeding prevention

The NICE guideline recommend that all patients should receive 1 g of tranexamic acid intravenously at the beginning of the surgery and 1 g at wound closure.^{22,23} Patients with an absolute contraindication to its use will not receive it and the reason will be documented.

2.5.3 Measuring Troponins for Cardiac Risk Assessment

We will suggest measuring troponin (I or T, high-sensitivity or not, as available to the institution) after hip fracture diagnosis (before surgery) and daily after surgery (POD 1 to 3), for the detection of myocardial injury.^{24,25}

2.5.4 Postoperative VTE prophylaxis

The American Society of Hematology (ASH) 2019 guidelines recommend that patients should receive daily VTE prophylaxis with LMWH or a DOAC starting ~12-24 hours after the surgery up to randomization.⁷ The study team will provide the required prescriptions, medications, and instructions prior to discharge, in consultation with the thrombosis service where available.

2.5.5 Pregnancy test

Pregnancy is an exclusion criterion, and rivaroxaban is contraindicated in pregnancy.²⁶ Therefore, pregnancy testing will be mandated for all individuals of child-bearing potential, prior to enrollment, unless it has already been performed for clinical reasons as part of standard of care.

2.6 Outcomes

2.6.1 Feasibility outcomes

The primary feasibility outcome will be the recruitment rate. Other feasibility outcomes will be complete 30 and 90 days follow up, treatment adherence. We will also measure the working time

for the research coordinator and research assistant, to obtain a precise estimate of the time commitments for the full-scale trial.

2.6.2 Progression criteria.

We will adopt a traffic light system for our feasibility outcomes: green (go) indicates that the criteria have been met and we should proceed, amber (amend) indicates that some changes should be made to proceed to the larger trial, and red (major amendments or stop) indicates that we should not move forward with the full-scale trial without major amendments.²⁷ Table 1 reports the formula for calculating the feasibility outcomes with the thresholds for progression. For recruitment rate, we aim at recruiting two (one) patients per month per site. For the 30 and 90 days follow up, we aim at 95% (85%) of the patients. For treatment adherence we aim at 85% (75%).

2.6.3 Exploratory clinical outcomes

The primary clinical outcome will be a composite of all-cause mortality, MI, non-hemorrhagic stroke, peripheral arterial thrombosis, and symptomatic, objectively confirmed VTE (DVT and/or PE). These outcomes will be monitored from randomization and over the specified follow-up period and will also be analyzed as individual outcomes, with the addition of CV mortality. We will also collect data on the length of stay and on re-hospitalizations, as measures of resource utilization.

2.6.4 Exploratory safety outcomes

The primary safety outcome will be bleeding independently associated with mortality after non-cardiac surgery (BIMS).²⁸ Secondary safety outcomes will be major bleeding events as defined by the ISTH, clinically relevant nonmajor bleeding, and minor bleeding.^{29,30}

The appendix contains detailed outcomes definitions.

Decisions regarding holding or discontinuing (and eventually restarting) either study drug rest with the attending physician and the patient. If a patient experiences a life-threatening or clinically relevant bleed, study personnel will recommend that the patient have their trial medication(s) held until the bleeding is stabilized. If a patient experiences a minor bleed, physicians may continue, temporarily interrupt, or permanently discontinue the trial medication. It is not a requirement, however, that the study medication is stopped for minor bleeding. The study personnel will be available for discussion about the best course of action. Participants will continue to be followed up for outcomes by the study team, unless they choose to withdraw from the study entirely.

2.7 Recruitment

Physicians and nurses working in the orthopedic, thrombosis and perioperative services (as appropriate and applicable for each site) will receive training on the HIPSTER study from the local investigators and study material prepared centrally. Health care providers who are part of the circle of care will identify potential participants, and if the potential participant provides permission to be approached for the study, the study team will be notified to seek informed consent. At sites where allowed by local policies, trained study personnel will also screen patient

charts for potentially eligible patients and approach where appropriate. If an eligible patient is missed, the research staff will discuss with the relevant stakeholders to reduce the potential for this to reoccur. A screening log will be kept as allowed per local institutional practices to document missed patients.

2.8 Participant timeline

The study schedule is reported in Figure 3.

Randomization will occur three to five days after surgery and will be timed to allow starting the intervention as soon as possible after allocation. The study personnel will follow patients throughout their hospital stay assessing the participants and reviewing their medical records, ensuring trial orders are followed, and noting any outcome. The study personnel will contact the patients via telephone (or in person, if the patient will not be discharged) 30 and 90 days after randomization and will obtain documentation as appropriate.

2.9 Sample size

For this study, we set the target of enrolling 100 patients as a pragmatic sample size. This will allow us to show a complete 90-day follow-up in 95% of participants with a 95% CI ranging from 89% to 98%. We also calculated possible sample sizes for the full-scale trial. **Table 2** reports the sample size for different scenarios. We used the rate of cardiovascular events reported in the HIP-ATTACK trial: 0.18 overall, 0.30 in the subgroup with myocardial injury. For the effect size, we used the one reported in the COMPASS study, adding a more conservative and a more optimistic estimate. This provides the rationale for only including people with myocardial injury.

2.10 Assignment of the interventions

Participants will be randomized to a control or experimental group with a 1:1 ratio using a computer-generated randomization schedule. The allocation sequence will be generated by a statistician and imported into the web application Research Electronic Data Capture (REDCap), which will function as a web-based randomization system and data collection tool. Participants will be stratified by center and the use of ASA at baseline or at the time of enrolment (yes or no). The stratification will be implemented using permuted blocks of variable size in random order, to ensure allocation concealment. Randomization will occur after a patient is deemed eligible and provides informed consent.

2.11 Blinding

The care providers, on-site study personnel, and participants will not be blinded to the treatment allocation, the outcome adjudicators will be.

2.12 Data collection and management

All data collection and management will be performed in accordance with International Council for Harmonisation - Good Clinical Practice (ICH-GCP) and applicable local privacy and personal health information protection regulations to maintain patient confidentiality and privacy. Each patient will be assigned a unique study ID and no direct patient identifiers will be collected as part of the study data. No patients will be recruited before institutional approval is obtained. The study personnel at participating sites will input the data into online CRFs through REDCap. REDCap is a browser-based, meta-driven electronic data capture (EDC) software and workflow methodology for designing clinical research databases. REDCap can be installed in a variety of

environments for compliance with standards such as Health Insurance Portability and Accountability Act (HIPAA) and FDA 21 CFR Part 11. Within REDCap, user privileges are utilized to maintain data integrity and confidentiality (e.g. each user has an individual account with unique username and password; a site research coordinator will only be able to access data from their site). REDCap implements authentication to validate the identity of end-users that log in to the system, as well as an auto-logout feature after a period of inactivity. REDCap has a built-in audit trail that automatically logs all user activity and logs all pages viewed by every user. The Computer Services Unit at McMaster University has the appropriate license agreement and is password protected on a secure site and on a separate server. Any hard copy documents will be stored in a locked, secure location at each site with access restricted to the study team only.

2.13 Statistical analysis

Baseline patient characteristics will be reported using means and standard deviations or medians and ranges as appropriate for continuous variables, and percentages with 95% CI for dichotomous and categorical variables. Feasibility and clinical outcomes will be reported using percentages with 95% CI. We will not look at clinical outcomes by group, as data from this feasibility study will be included in the analysis of a later full-scale multicenter study if its design will not change.

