2.14 Monitoring

Both rivaroxaban and ASA are approved for prevention of arterial and venous thrombosis and have been extensively used, and the combination of low dose rivaroxaban and ASA is approved for prevention of arterial thrombosis. The overall adverse profiles of each agent and in

combination have been well described in broad populations, with the most common side effect being bleeding. Given the approved status and known risk profiles of rivaroxaban and ASA as well as the small sample size of this pilot study, we are not planning to set up a data monitoring committee, nor to implement formal interim analyses. However, at 50% recruitment, we will ask a person with expertise in cardiovascular medicine and clinical trials to review the event rates. This person will be independent of the study team. If there is a safety concern, the study will be paused and the protocol will be reconsidered. If there is no major concern, the study investigators will remain blinded.

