2.14.2 Protocol-specific exceptions to expedited SAE reporting

For the purpose of this trial, expected events will be captured on the CRFs as study outcome events only and will be exempted from the expedited reporting but will be included in the final study report. This includes:

• Primary or secondary efficacy outcomes for the full trial:

- Overall mortality
- Cardiovascular mortality
- All thrombosis or thromboembolism (arterial and venous)
- Hospitalization

• Safety outcomes:

Bleeding events

- Expected Events: Events that are expected to occur in high frequency in the population under study, including:
 - Planned hospitalization (e.g., surgery, rehabilitation, respite care)
 - Conditions e.g., chronic obstructive pulmonary disease, hypertension, diabetes
 and trauma

The sponsor will report all serious unexpected adverse drug reactions (SUADRs) to the regulatory authorities and REB. If the SUADR is neither fatal nor life-threatening, the sponsor will report the SUADR to Health Canada within **15** calendar days of awareness. If the SUADR is fatal or life-threatening, Health Canada will be advised within **7** calendar days of awareness. Follow-up reports will be submitted as required. In addition, as required by ICH-GCP, the sponsor will expedite reporting of all SUADRs to all concerned institutions and REBs.

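### Section 2.13 bars by-arm clinical outcomes outright for a reason that is only conditional, and no aggregate by-arm safety review follows the 50% look

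*Protocol*

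**What the plan says.** Section 2.13 (Statistical analysis) plans that "Feasibility and clinical outcomes will be reported using percentages with 95% CI". It then says "We will not look at clinical outcomes by group, as data from this feasibility study will be included in the analysis" and finishes the sentence with "of a later full-scale multicenter study if its design will not change". It does not say what is reported if the design does change or if no full trial follows.

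Section 2.14 (Monitoring) says "we are not planning to set up a data monitoring committee, nor to implement formal interim analyses". Its substitute is a single review: "at 50% recruitment, we will ask a person with expertise in cardiovascular medicine and clinical trials to review the event rates". The reviewer is independent of the study team, and a safety concern pauses the study. Otherwise "If there is no major concern, the study investigators will remain blinded". The text does not state that the rates are reviewed by arm, although the remark about blinding suggests it.

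Section 2.6.2 (Progression criteria) bases the decision on feasibility outcomes: "green (go) indicates that the criteria have been met and we should proceed". Table 1 sets thresholds for recruitment, follow-up and adherence only. Amber and red both foresee amendments.

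Section 2.14.2 treats deaths, thrombosis and bleeding as expected outcome events. They "will be exempted from the expedited reporting but will be included in the final study report", with no mention of arm.

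**The concern.** Withholding by-arm results from investigators is sound practice while the pilot data may still enter the full trial. The difficulty is that the rule is written without a condition while its only justification has one. Under amber or red the protocol itself expects changes, and some of these could end the roll-in. Followed to the letter, section 2.13 would then still forbid a by-arm description after the reason for forbidding it has gone.

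If the trial proceeds unchanged, the gap is different. Nothing after the half-way look gives anyone outside the study team an aggregate view of harm by arm before progression is decided.

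This matters because bleeding is the main hazard on the protocol's own account. Section 1.1 cites hazard ratios for major bleeding of 1.70 (COMPASS) and 1.42 (VOYAGER PAD) for this regimen against ASA alone. The intervention runs for 90 days against up to 30 in the control arm, so a pooled percentage cannot show in which arm bleeding arises.

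**Working it through.** The plan gives no figure on this point. The check is mainly textual, with arithmetic to size the gap.

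**1. The rule beside its reason.**
- Rule (2.13): no by-group clinical outcomes, with no exception.
- Reason (2.13): inclusion in the full-scale analysis, if the design is unchanged.
- Cases: (a) full trial with unchanged design: the reason holds; (b) full trial with changed design: it lapses; (c) no full trial: it lapses. The protocol states no fallback for (b) or (c).

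**2. Who is outside the one review.** Inputs: 100 participants (2.9), 1:1 allocation (2.10), review at 50% recruitment (2.14).
- Randomised after the review: 100 − 50 = 50, about 25 per arm.
- Of the first 50, some are still in follow-up. The number of sites is not given, so I assume 2 to 10 sites and steady accrual at Table 1's 1 or 2 per site per month. Number with 90 days complete when the 50th is randomised = 50 − (sites × rate × 90/30.44), floored at zero.
  - 2 sites at 1 per month: 50 − 2 × 2.96 ≈ 44.
  - 5 sites at 2 per month: 50 − 10 × 2.96 ≈ 20.
  - 10 sites at 2 per month: 20 × 2.96 ≈ 59, which exceeds 50, so 0.

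**3. Expected events.** Inputs from 1.1: major bleeding about 5%; 90-day mortality 9.5% in unselected hip fracture patients.
- Major bleeds per arm: 0.05 × 25 = 1.25 for those enrolled by the half-way look; 0.05 × 50 = 2.5 at the end (95% binomial prediction range 0 to 6).
- Deaths per arm at the end: 0.095 × 50 = 4.75 (range 1 to 9).

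**4. What pooling hides.** With 50 per arm, risks of 5% and 15% give 2.5 + 7.5 = 10 expected bleeds in 100. Risks of 10% in both arms give 5 + 5 = 10. The pooled result is the same 10%.

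**5. What a by-arm table could show.** Illustrative two-sided 5% power, normal approximation (rough at these counts), with p̄ the mean of the two risks:

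power = Φ{[(p2 − p1) − 1.96 √(2p̄(1 − p̄)/n)] / √[(p1(1 − p1) + p2(1 − p2))/n]}

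For 5% against 20% and n = 50: (0.15 − 1.96 × 0.0661)/0.0644 = 0.32, so power is about 62%.

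| Major bleeding | 25 per arm | 50 per arm |
|---|---|---|
| 5% v 10% | 10% | 15% |
| 5% v 15% | 21% | 38% |
| 5% v 20% | 36% | 62% |

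The alternative risks are my assumptions. The 25-per-arm column supposes complete follow-up, so it flatters the half-way look. No test is proposed; the table only shows how large an imbalance must be to become visible.

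**The case against.** Several points on the other side stand.

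- **The conditional clause may lift the bar.** The bar rests on roll-in, so one may read it as lapsing when roll-in does. That is a reasonable reading. The protocol does not state it, however, and it should not be left to interpretation. An analysis plan that is not shown could settle it.
- **Few events.** With about 2.5 major bleeds expected per arm, only a gross imbalance would be seen. This is correct, and it is why a formal safety threshold for green would be hard to defend.
- **Feasibility criteria need not carry a safety gate.** The traffic lights are for feasibility outcomes by design. This stands too, so the review should inform the decision and not become a criterion.
- **A by-arm look before roll-in is an interim look.** This has force for efficacy events, so the review should be confined to harm. Deaths also belong to the primary clinical composite. A look that can only raise a concern about harm cannot increase the overall chance of falsely claiming benefit, and the investigators stay blinded.

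A reader might also infer more than the documents support:

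- **That the by-arm data would be lost.** They stay in REDCap (2.12) and records are kept for 15 years (2.16). What is missing is a plan to report them.
- **That 2.14.2 exempts bleeding and deaths from expedited reporting because they appear in the final report.** It exempts them as expected events captured as outcomes; inclusion in the report is an added statement. Pooled reporting satisfies it, so 2.13 and 2.14.2 do not conflict.
- **That nobody sees events by arm.** The trial is open label (2.11), so site staff know their own patients' arms, and serious unexpected reactions are reported individually (2.14.1, 2.14.2). But under 2.12 a site coordinator sees only that site's data. The gap concerns aggregate by-arm data.

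**Conclusion.** The point holds in a limited form. Section 2.13 fixes an unconditional rule on a conditional reason. Read literally, it leaves bleeding and deaths pooled even when roll-in does not happen. If the full trial goes ahead, no aggregate by-arm safety review covers the 50 participants randomised after the half-way look, nor the remaining follow-up of the first 50. On assumed accrual, between 6 and all 50 of those would still be in follow-up.

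The consequence lies in safety oversight and reporting. It affects no sample size, power or error rate. The conclusion rests on the literal reading of 2.13, on 1:1 allocation, and on taking the 50% review to be by arm. If that review is pooled, the gap is wider. The change is worth making because it is cheap, but its yield is limited to gross imbalances.

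**What to change.** 1. **Section 2.13.** State that the bar applies only while inclusion of the pilot data in a full-scale trial remains possible. If they will not be included, because no full trial starts or its design changes, report clinical and safety outcomes by arm, descriptively, with 95% confidence intervals and no hypothesis tests.
2. **Section 2.14.** Add one closed review by the same independent person after the last 90-day contact and before the progression decision. It covers deaths and bleeding by arm, for harm only. The investigators are told only whether there is a concern, as at the 50% look. State that this informs the decision and is not a formal threshold for green. Say also whether the 50% review is by arm.

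**Cost:** protocol wording, one short additional review and, if there is no roll-in, one descriptive table. No extra participants are needed, and investigators see no by-arm results while roll-in is possible. The limitation to accept is that, with about 2.5 major bleeds expected per arm, the review can reassure only against a gross imbalance.

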2.14 Monitoring

Both rivaroxaban and ASA are approved for prevention of arterial and venous thrombosis and have been extensively used, and the combination of low dose rivaroxaban and ASA is approved for prevention of arterial thrombosis. The overall adverse profiles of each agent and in

combination have been well described in broad populations, with the most common side effect being bleeding. Given the approved status and known risk profiles of rivaroxaban and ASA as well as the small sample size of this pilot study, we are not planning to set up a data monitoring committee, nor to implement formal interim analyses. However, at 50% recruitment, we will ask a person with expertise in cardiovascular medicine and clinical trials to review the event rates. This person will be independent of the study team. If there is a safety concern, the study will be paused and the protocol will be reconsidered. If there is no major concern, the study investigators will remain blinded.

2.14.1 Documenting and Reporting of Adverse Events

An Adverse Event (AE), as defined by GCP, is any unfavorable and unintended sign (including an abnormal laboratory finding), symptom, or disease having been absent at baseline, or, if present at baseline, appears to worsen and is temporally associated with medical treatment or procedure, regardless of the attribution (i.e., relationship of event to medical treatment or procedure). Because of the extensive safety data available on ASA, rivaroxaban, and their combination, AE collection in HIPSTER pilot is limited to changes in health status that require permanent drug discontinuation. This ensures that only those events the investigator thinks are related to the study medication are considered an adverse event. These AEs will be collected during the whole treatment period, and will be followed to resolution or stabilization. Data on AEs will be collected during the hospital stay and at the follow-up assessments. Moreover, study participants will be able to report AEs by contacting their local study team or the coordinating center.

A serious adverse event (SAE) is classified as any untoward medical occurrence that, at any dose, results in death, is life-threatening, requires inpatient hospitalization or prolongation of existing hospitalization, results in persistent or significant disability / incapacity, is a congenital anomaly / birth defect and/or is another medically important serious event representing a significant hazard, which is comparable to the aforementioned criteria.

All unexpected and related or possibly related SAEs will be reported by the site PI to their local REB within 7 business days of awareness. The sponsor will report these SAEs to HiREB within 15 business days of awareness if they require a change to the research and/or informed consent form and/or requires immediate notification to participants for safety reasons. Follow-up reports will be submitted as required.

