2.4 Trial intervention

Intervention Arm: Patients randomized to the intervention will receive rivaroxaban 2.5 mg orally BID and ASA 75-100 mg OD for 90 days, to be started between postoperative day (POD) three and five. The exact dose of ASA will depend on local formulary and clinical practice at each participating site. A maximum of four postoperative days of any anticoagulant (LMWH, UFH, fondaparinux or a DOAC) will be allowed in the meantime.

Control Arm: Patients in the control arm will receive the institution's standard of care for thromboprophylaxis for up to 30 days. While the study team will encourage a 30-day duration to align with guideline recommendations and ensure consistency with the intervention arm, it will not be mandated as there are variations in the duration of postoperative VTE prophylaxis across institutions. Actual practices at each site will be documented and analyzed. The following regimens are provided as guidance only, and actual clinical practices will be recorded and analyzed.

Low-molecular-weight heparin (LMWH)

- Enoxaparin: 40 mg subcutaneously OD (or 30 mg subcutaneously BID);
- Dalteparin: 5000 IU subcutaneously OD (or alternative dosing based on institutional protocol);
- Tinzaparin: 4500 IU subcutaneous OD;
- Fondaparinux: 2.5 mg subcutaneously OD; or
- **Direct oral anticoagulant (DOAC):** Rivaroxaban 10 mg OD or apixaban 2.5 mg BID, started after surgery or after a period of LMWH.

2.4.1 People already on ASA:

For people already on ASA at the time of the hip fracture diagnosis, who are eligible for the study, we will suggest holding it preoperatively. In the intervention arm, ASA will be restarted as planned after randomization. In the control arm, if the indication to ASA is confirmed, it can be restarted at physician's discretion.

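### Section 2.14.1 contradicts its own adverse event definition, and its permanent-discontinuation limit leaves a related non-outcome SAE with a reporting duty but no stated capture route

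*Protocol*

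**What the plan says.** Protocol Section 2.14.1 makes four statements in sequence.

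- **Definition.** It takes the GCP definition of an AE, which applies "regardless of the attribution (i.e., relationship of event to medical treatment or procedure").
- **Collection limit.** "AE collection in HIPSTER pilot is limited to changes in health status that require permanent drug discontinuation". The reason given is the large body of safety data on the two drugs and their combination.
- **Claimed effect of the limit.** "This ensures that only those events the investigator thinks are related to the study medication are considered an adverse event".
- **Serious events.** SAEs are defined by the usual seriousness criteria, with no condition on what happens to study drug. "All unexpected and related or possibly related SAEs will be reported by the site PI to their local REB", within 7 business days.

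Section 2.14.2 deals with exceptions to expedited SAE reporting. For deaths, thrombosis, hospitalization, bleeding and some expected conditions, "expected events will be captured on the CRFs as study outcome events only", and these go into the final report. It also requires the sponsor to report all serious unexpected adverse drug reactions (SUADRs), to Health Canada within 7 or 15 calendar days depending on severity. That duty does not depend on discontinuation either.

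Section 2.6.4 leaves holding, stopping and restarting study drug to the attending physician and the patient. For a life-threatening or clinically relevant bleed, "study personnel will recommend that the patient have their trial medication(s) held until the bleeding is stabilized".

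The abbreviation list expands AE and SAE with the word reaction, whereas Section 2.14.1 speaks of events.

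**The concern.** A site needs three separate rules: what an AE is, which AEs and SAEs go on the case report form, and which must be reported quickly. Section 2.14.1 runs the first two together. It starts from a definition that ignores cause and ends by admitting only events thought to be related. The link between them is a claim that permanent discontinuation guarantees relatedness, which it does not.

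Two things are at stake. First, the discontinuation filter stands in for a relatedness judgement that the protocol never asks the investigator to record for each event, although the SAE and SUADR duties depend on that judgement. Second, the only stated collection rule is narrower than the reporting duty. Section 2.14 sets up no data monitoring committee, only one independent look at event rates at 50% recruitment, so the site's own record is the main route by which an unexpected reaction would be noticed. A later analysis plan cannot recover events that were never written down.

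**Working it through.** The point rests on no figure in the plan, so there is nothing to recompute. The check is to take each type of event through the rules in Sections 2.6.3, 2.6.4, 2.14.1 and 2.14.2.

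| Event | AE by the definition? | Inside the collection limit? | Passes the relatedness sentence? | Reporting duty or other capture |
|---|---|---|---|---|
| A. Unrelated, not an outcome, study drug stopped for good | Yes | Yes | No | None stated |
| B. Related, non-serious, not an outcome, drug held and restarted | Yes | No | Yes | None stated |
| C. Related, unexpected, serious, not an outcome, drug held and restarted | Yes | No | Yes | Must be reported (2.14.1; also 2.14.2 if a SUADR); no stated capture route |
| D. Bleed, drug held and restarted | Yes | No | Depends on the investigator | Safety outcome (2.6.4); final report (2.14.2) |
| E. Bleed, drug stopped for good | Yes | Yes | Depends on the investigator | Safety outcome; 2.14.2 directs it to outcomes only |
| F. MI or VTE, whatever happens to the drug | Yes | Only if the drug is stopped for good | Depends on the investigator | Part of the primary clinical composite (2.6.3), monitored from randomization over follow-up |

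**Row A** refutes the claimed effect directly. The event satisfies the definition and the collection limit, yet it is not related, so the limit has not ensured what Section 2.14.1 says it ensures.

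**Row B** shows the failure in the other direction. A deliberate limit on collecting non-serious AEs is permissible, so leaving this event out is not an error in itself. It does show that the filter also discards related events and cannot serve as a measure of relatedness.

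**Row C** is the practical gap. Neither the SAE duty nor the SUADR duty depends on discontinuation. The only sentence on what is collected does, and no sentence says that SAEs are recorded outside it. The explicit hold recommendation in Section 2.6.4 concerns bleeds, which are outcomes. The same section's general statement on holding and restarting covers other reactions, so row C can occur under the protocol.

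**Rows D to F** mark where the problem stops. Every grade of bleeding is a safety outcome, and MI and VTE belong to the clinical composite. Their AE status does not decide whether they are recorded.

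The abbreviation list is a separate inconsistency. A reaction implies cause, so the list agrees with the relatedness sentence and disagrees with the definition.

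**The case against.** The strongest reply is that Section 2.14.1 contains one definition, one legitimate limit on collection and one badly reasoned sentence. Much of this stands. A reader might infer that the protocol offers four rival AE definitions, but the discontinuation rule only limits collection, and Section 2.14.2 only exempts events from expedited reporting. Neither defines an AE. The contradiction is between the definition and the relatedness sentence.

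A reader might also infer that a bleed or an MI could be counted or dropped according to which sentence a site follows. Sections 2.6.3, 2.6.4 and 2.14.2 rule that out: these events are recorded as outcomes and appear in the final report. For a bleed that ends treatment, the direction to outcomes only is most naturally read as a specific exception to Section 2.14.1.

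A third tempting step is to add the background rates in Section 1.1 (MI 5.5%, VTE 1.1%, major bleeding about 5%) to get 5.5 + 1.1 + 5.0 = 11.6 per 100 participants classified inconsistently. This does not hold. It assumes that every such event ends treatment, and it takes 90-day rates from patients not selected for myocardial injury. Those are also outcome events, which are captured anyway. Nor can exclusion 2c be used to argue that a new MI or VTE forces discontinuation, because it is an entry criterion and not a stopping rule.

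Finally, the SAE gap is narrow. SAEs have their own definition, staff follow patients in hospital and contact them at 30 and 90 days, and re-hospitalizations are collected. But Section 2.6.3 collects re-hospitalizations as a measure of resource use, with no stated relatedness judgement. They also do not cover an SAE that is serious for another reason, such as a prolonged index stay or lasting disability. The gap is reduced, not closed.

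**Conclusion.** The point holds in a limited form. Section 2.14.1 contradicts itself on whether relatedness is part of an AE, and permanent discontinuation does not track relatedness in either direction. A related, unexpected SAE that is not a trial outcome and is managed by a temporary hold has a reporting duty but no stated route by which it is recorded. The abbreviation list needs to be brought into line.

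The size cannot be stated as a number. The events at risk are non-outcome events, and the protocol gives no rate for them. Section 2.13 specifies no AE analysis and no progression criterion uses an AE count, so the feasibility conclusions are unaffected. The consequence lies in safety capture and reporting.

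The conclusion assumes that no other instruction to sites, such as a case report form guide, already has SAEs recorded whatever the drug status. The protocol mentions none.

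**What to change.** In Section 2.14.1:

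1. Delete the sentence claiming that the discontinuation limit ensures relatedness, and have the investigator record relatedness for each AE and SAE.
2. Apply the permanent-discontinuation limit to non-serious AEs only. State that SAEs other than the outcome and expected events listed in Section 2.14.2 are recorded whether or not study drug is stopped.
3. Reconcile the abbreviation list with Section 2.14.1, so that AE and SAE mean event in both places.

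This keeps the sponsor's lighter collection for well-known drugs and the existing handling of outcome events, and it changes no treatment rule. The cost is some wording, one relatedness item on the case report form, and a few more non-outcome SAEs to record among 100 participants. It should be done before sites start recording, because missed events cannot be reliably reconstructed.
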